4.5.4 Stopping Criteria for Dose Escalation

1. Progressing from a dosing regimen cohort to the next or from a study part to the next will not occur in the presence of moderate or severe drug-related ocular AEs in 2 or more SHP639-treated subjects in a given cohort.
2. If 1 or more subjects experience corneal hazing of grade 3 or greater on the Hwang Grading Scale of Corneal Haze, they will be discontinued from the study. At that time, the study will stop for further evaluation by the Shire's Dose Escalation Committee.

3. If 2 or more subjects in a given cohort receiving active drug have a severe AE in the same organ or body system, no further subjects will be enrolled or dosed until further evaluation of the available data is made by the medical monitor and investigator to determine whether to stop or proceed with the study. Following a safety review of the event, study enrollment or dosing of currently enrolled subjects may be restarted if the medical monitor and the investigator determine that it is safe to proceed with the study.
4. If any other drug-related event occurs in subjects receiving active drug and is deemed to pose an unacceptable risk to subjects by the investigator or medical monitor after further evaluation, no further subjects will be enrolled or dosed until further evaluation of the available data is made by the medical monitor and investigator to determine whether to stop or proceed with the study. Following a safety review of the event, study enrollment or dosing of currently enrolled subjects may be restarted if the medical monitor and the investigator determine that it is safe to proceed with the study.

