Shire's Dose Escalation Committee will consist of, at a minimum, the coordinating principal ophthalmologist, the Shire medical monitor, and the Shire ophthalmic study physician. Additional team members may be included as needed.

At any time during the course of the study, subjects will be discontinued from the study if their IOP measurement reaches a reading of greater than 36 mmHg or a reading of less than 8 mmHg. Additionally, if subjects experience corneal hazing of grade 3 or greater on the Hwang Grading Scale of Corneal Haze, then they will be discontinued from the study. Should an event occur that requires a subject's discontinuation from the study, the study will be halted for further evaluation by Shire's Dose Escalation Committee.

The Dose Escalation Committee may authorize progression from 1 cohort to the next after the completion of the previous treatment regimen cohort and completion of the previous dose level cohort, as appropriate. Additionally, more than 1 cohort of safety data may be reviewed at a dose escalation meeting depending on scheduling and study progress. A minimum of 6 subjects should have completed the previous cohort(s) without clinically significant adverse changes; this includes findings on the ophthalmologic examination. Additionally, progression will not occur in the presence of moderate or severe drug-related ocular AEs in 2 or more subjects.

If, in the judgment of the coordinating principal ophthalmologist, the Shire medical monitor, and the Shire ophthalmic study physician, it is unclear whether there is a potential safety concern or whether dose escalation should occur, a dose level may be reduced, modified, or repeated depending on the outcome of the safety data review between doses or treatments. Further, based on the findings from the dose escalation review meetings, a cohort (or cohorts) may be determined to not be necessary to determine the safety of SHP639. Finally, upon completion of all dose cohorts, additional doses may be studied based on emergent safety, PD, and PK data following the necessary protocol amendment and Institutional Review Board (IRB) reviews.

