6.2.4 Unmasking the Treatment Assignment

The treatment assignment code must not be broken during the study except in emergency situations where the identification of the investigational product is required for further treatment of the subject. The investigator should contact the medical monitor as soon as possible after the investigator has been unmasked.

In the event that the treatment assignment code is broken and the date and signature of the person who broke the code are recorded in the IRT and the source documents. The reason for breaking the code will be captured in the clinical database. Upon breaking the code, the subject is withdrawn from the study but should be followed up for safety purposes. Any code breaks that occur must be reported to the contract research organization (CRO) and sponsor. Code-break information is held by the pharmacist/designated person at the site.

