9.3 Data Handling Considerations

Data that may potentially unmask the treatment assignment (ie, investigational product blood concentrations, antidrug antibody, treatment allocation, and investigational product preparation/accountability data) will be handled with special care during the data cleaning and review process. These data will be handled in such a way that, before unmasking, any data that may unmask study team personnel will be presented as masked information or otherwise will not be made available. If applicable, unmasked data may be made available to quality assurance representatives for the purposes of conducting independent drug audits.

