9.5 Planned Interim Analysis, Adaptive Design, and Dose Escalation Committee

Shire's Dose Escalation Committee will be convened consisting of the coordinating principal ophthalmologist and Shire medical monitor. Ad hoc study team members can be included such as biostatistics, pharmacokinetics, drug safety, and clinical operations if needed. The committee will review collective safety data for Cohort A and Cohort B to decide whether Part 2 in the same dose level and Part 1 in the next dose level (concentration) can commence.

An unmasked interim analysis (IA) will be performed after cohorts A1, A2, A3, B1, B2, and B3 have completed through Day 29 of the B3 cohort. Data from sites will be entered into the database, queried, and discrepancies resolved. There is no intention to stop early based on data from the IA. The intent of this IA is to determine if the escalated doses have identified a pharmacodynamically significant safe and tolerable dose(s) for further clinical evaluation.

Team members reviewing the interim analysis will be reviewing unmasked data from cohorts A1, A2, A3, B1, B2, and B3. The SAP will be finalized before data are frozen for this interim analysis.

All cohorts conducted after B3 (ie Part 1 of the study) may be unmasked following completion of Day 29 to permit review of safety, tolerability and the pharmacodynamics effects of each cohort to better inform planning for additional cohorts and further clinical development options for SHP639.

A final unmasked analysis will be conducted when all subjects of the remaining cohorts have completed through Day 29. The Day 88/FU visit is the planned study completion for each subject.

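### The mandatory pause for two severe AEs (Protocol 4.5.4 item 3) counts only active-drug subjects, which the masked staff who apply it cannot do

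*Protocol*

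**What the plan says.** Protocol 4.5.4 lists four stopping criteria. Item 3 begins "If 2 or more subjects in a given cohort receiving active drug have a severe AE in the same organ or body system". When it is met, nobody further is enrolled or dosed "until further evaluation of the available data is made by the medical monitor and investigator", and those two may then allow a restart. Item 1 blocks progression on "moderate or severe drug-related ocular AEs in 2 or more SHP639-treated subjects in a given cohort". Item 4 is also limited to subjects on active drug but turns on a judgement of unacceptable risk. Item 2 concerns corneal haze and has no arm condition.

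On masking, 6.1.1 describes a double-masked study with matching product. Section 6.2.4 says: "The treatment assignment code must not be broken during the study except in emergency situations where the identification of the investigational product is required", the purpose being that person's own care. It adds: "Upon breaking the code, the subject is withdrawn from the study but should be followed up for safety purposes". Section 9.3, on data cleaning and review, says that before unmasking "any data that may unmask study team personnel will be presented as masked information or otherwise will not be made available". Under 9.5, Cohorts A1 to B3 are unmasked at an interim analysis after Day 29 of B3, and later cohorts "may be unmasked following completion of Day 29 to permit review of safety". Dosing ends on the morning of Day 28 (6.2.3.1, 7.1.2.2).

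Section 6.2.3.2 restates item 1 without the arm restriction: "Additionally, progression will not occur in the presence of moderate or severe drug-related ocular AEs in 2 or more subjects". It also asks for at least 6 subjects to complete the previous cohort without clinically significant adverse changes, and halts the study after an event that requires a subject's discontinuation.

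**The concern.** Item 3 is written as an automatic trigger, but its count needs treatment assignments that its users do not have while subjects are being dosed. Checking a stopping rule is not among the reasons for a code break in 6.2.4, and a code break withdraws the subject. Within 4.5.4, item 3 is also the only rule based on a count that reaches severe nonocular events.

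This is a first-in-human study. Table 7 of the protocol puts the daily-dose margin for the 0.6% solution at 1.3-fold BID, about 1-fold TID and 0.6-fold QID. A mandatory stop in that setting should work on the data its users can see. Otherwise, when two masked subjects have severe events in one system, whether dosing pauses depends on discretion and not on the rule.

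**Working it through.** The plan gives no operating figure for this rule, so there is none to reproduce.

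**Is the allocation known when the rule must be applied?**
- Last dose: morning of Day 28 (6.2.3.1, 7.1.2.2).
- Earliest planned unmasking: after Day 29 of the cohort for those conducted after B3, and after Day 29 of B3 for Cohorts A and B (9.5).
- Exception: an emergency code break for an individual subject's treatment (6.2.4).
- Unmasked role for the rule: none. Section 6.2.4 places code-break information with the site pharmacist or a designated person, but gives that person no part in item 3.

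**How informative is the masked count?** Inputs: 5 active and 2 placebo per cohort (9.6), with no replaced or added subjects.

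Exactly 2 affected, event unrelated to arm, C(7,2) = 21 allocations:
- both active: C(5,2) = 10, so 10/21 = 48%; item 3 is met
- one in each arm: 5 × 2 = 10, so 10/21 = 48%; not met
- both placebo: C(2,2) = 1, so 1/21 = 5%; not met

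Exactly 3 affected, no arm effect: [C(5,2) × 2 + C(5,3)] / C(7,3) = (20 + 10)/35 = 86% met. With 4 or more affected, at least 2 must be active, because only 2 subjects are on placebo.

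If SHP639 multiplies the odds of the event by w (assumed), then with 2 affected P(both active) = 10w² / (10w² + 10w + 1):
- w = 3: 90/121 = 74%
- w = 5: 250/301 = 83%
- w = 10: 1000/1101 = 91%

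**Sensitivity to cohort make-up.** Replacements (4.5, 6.2.2) and enlargement (9.6) change these figures. With 5 active and 3 placebo, 2 affected gives 10/28 = 36% and 4 affected gives 65/70 = 93%. With 6 active and 2 placebo, 2 affected gives 15/28 = 54%.

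**What would counting everyone cost?** The plan states no severe-AE rate, so p, the chance per subject in one body system, is assumed. For n subjects, P(2 or more) = 1 − (1−p)ⁿ − np(1−p)ⁿ⁻¹.

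| p, same in both arms | 2 or more of 5 active | 2 or more of all 7 |
|---|---|---|
| 5% | 2.3% | 4.4% |
| 10% | 8.1% | 15.0% |
| 20% | 26.3% | 42.3% |

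If placebo subjects never have the event, the two counts trigger equally often.

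**Does another provision supply the same pause?**
- The 6.2.3.2 ocular-AE sentence and the 6-completer condition act on progression to the next cohort, not on dosing in the current one.
- The 6.2.3.2 halt needs an event that requires discontinuation. The severity definition in 8.1.1 does not make a severe AE such an event.
- The sponsor's power to suspend (10.1.4) is discretionary.

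**The case against.** The strongest reply is that subjects are better protected than item 3 alone suggests. The 6.2.3.2 halt has no arm condition and needs only one subject, so for events that require discontinuation it is stricter than item 3. The sentences before it concern IOP limits and haze, so it may be confined to those, but as worded it can be read generally. In a cohort of 7, two clinically significant adverse changes leave 5 clean completers, short of the 6 needed to progress. The sponsor may suspend all or part of the study at any time (10.1.4), and either sponsor or investigator may withdraw a subject for safety (4.5). Item 3 does not forbid an earlier pause.

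All of this stands, and it rules out three stronger readings that a reader might infer:
- *Item 3 can never be applied during dosing.* Some severe AEs could justify an emergency code break, and in an intact cohort 4 affected subjects meet the rule without unmasking.
- *Staff must either guess or break codes.* They can pause by choice; only the mandatory trigger is undetermined.
- *Subjects have no all-subject protection.* The 6.2.3.2 provisions are such protection, for other triggers or for progression only.

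The practical stakes are also limited. Section 1.2.1 reports very low to nondetectable systemic exposure in the nonclinical topical studies. The Cohort B3 repeat had its interim analysis in June 2018 (SAP 13), so an edit would serve cohorts after that one. None of this makes a pause mandatory in the remaining case.

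**Conclusion.** The point holds in a limited form. For two severe AEs in the same system that do not require discontinuation, the mandatory pause in item 3 turns on assignments that the medical monitor and investigator do not normally have during dosing, and no unmasked person is named to supply them. With exactly 2 affected subjects the criterion is met in 48% of allocations if the event is unrelated to arm, and in 74% to 91% at assumed odds ratios of 3 to 10. With 3 affected and no arm effect it is met in 86%.

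The 48% and 86% follow exactly from an intact 5:2 cohort and shift if subjects are replaced or added. The odds ratios and severe-AE rates are assumptions. The documents support a flaw in one stopping rule, with partial cover elsewhere. They do not support a claim that dosing is unprotected. It is worth correcting because the rule is meant to act automatically in a first-in-human study and the correction is small.

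**What to change.** In Protocol 4.5.4 item 3, replace *receiving active drug* with *regardless of treatment assignment*, so that the pause triggers on masked data. In item 1, delete *SHP639-treated* so that it agrees with 6.2.3.2. The same edit to item 4 is optional, because that item rests on judgement and not a count. Leave the 6.2.3.2 halt sentence as it is.

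Do not instead appoint an unmasked person who reports only whether the active-drug criterion is met. With exactly 2 affected subjects, a positive report tells the team that both are on SHP639 and unmasks them.

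The cost is protocol wording plus some pauses triggered by placebo subjects. At equal rates in both arms the added chance per cohort is 4.4% − 2.3% = 2.1 percentage points at an assumed 5% rate, and 15.0% − 8.1% = 6.9 points at 10%. Item 3 already lets the medical monitor and investigator restart after review.

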5. PRIOR AND CONCOMITANT TREATMENT

5.1 Prior Treatment

Prior treatment includes all treatments (including but not limited to prescription treatments, investigational products, vitamins, herbal treatments, and nondrug therapies) received within 30 days or 5 half-lives (whichever is longer) before the date of the first dose of investigational product and any procedures performed within the 5 years before the date of the first dose of investigational product. Prior treatment information must be recorded on the appropriate eCRF page.

5.2 Concomitant Treatment

Concomitant treatment refers to all treatment and ocular procedure received between the dates of the first dose of investigational product and the end of the follow-up period, inclusive. Concomitant treatment information must be recorded on the appropriate eCRF page.

5.2.1 Permitted Treatment

Subjects should refrain from taking any medications (excluding those medications listed below) during the course of the study, until after discharge from the site on Day 29 of the MDTP; refer to Section 5.2.2 for details. Any medication that is considered necessary for the subject's safety and well-being may be given at the discretion of the investigator. The administration of all medications (including investigational products) must be listed on the appropriate eCRF page.

The following medications are permitted during the study:

- A stable dose (defined as at least 4 weeks) of prescription medication for chronic use (with the exception of those medications listed in Section 5.2.2, [Table 8](#)), including but not limited to:
 - Hormonal contraceptives for females of childbearing potential administered according to the package insert (see Section 4.4.1)
 - Hormone replacement therapy
 - Antihypertensive medication if the subject is on a stable dose for at least 4 weeks
 - A stable dose (defined as at least 4 weeks) of medication that can substantially alter IOP (with the exception of those medications listed in [Table 8](#))
- Occasional use of acetaminophen (paracetamol) and ibuprofen

Refer to Section 5.2.2 for information on use of artificial tears.

5.2.2 Prohibited Treatment

[Table 8](#) details the washout period (relative to randomization) for common prior medications that are excluded for this study. Refer to Section 7.1.1.3 for details of the washout period for prohibited medications. Subjects must not take these medications until after discharge from the site on Day 29 of the MDTP, at which time they may resume taking their usual medication.

Table 8 Common Excluded Medications and Associated Washout Period

Medication	Minimum Time Before Randomization				
	7 days	14 days	28 days	3 months	1 year
Steroids (except for nonperiocular dermatologic use)				X	
Belladonna alkaloids (scopolamine, hyoscyamine, atropine)	X				
B-type natriuretic peptides (eg, nesiritide)					X
Prostaglandins			X		
β -adrenoceptor antagonists (eye drops)			X		
α -adrenergic agonists (eye drops)			X		
Epinephrine-related medications (eye drops)			X		
Carbonic anhydrase inhibitors (eye drops)	X				
Pilocarpine (all drops)	X				
Carbachol (eye drops)			X		
Echothiophate (eye drops)			X		
Glycerol	X				
Mannitol	X				
Theophylline		X			
Amantadine			X		

The use of all preserved artificial tears and any ocular gels and other lubricants is **prohibited** at all times during the study.

The use of **nonpreserved** artificial tears is **prohibited** during the following intervals, which include study visits:

- Cohort A, SDTP: Day -2 to Day 2, after final assessment
- Cohort A, MDTP: Day -2 to Day 29, after final assessment
- Cohorts B, C, and D: Day -2 to Day 29, after final assessment

The use of **nonpreserved** artificial tears is **allowed only during washout periods**, according to the schedule below.

- Cohort A, SDTP, Washout 1: Start of screening until the evening of Day -2, SDTP
- Cohort A, Washout 2: Day 2 after last assessment until the evening of Day -2, MDTP
- Cohorts B, C, and D, Washout 1: Start of screening until the evening of Day -2

Refer to Section [4.3](#) for restrictions on the use of alcohol, tobacco, caffeine, and xanthine.

Other medications not listed in [Table 8](#) may be considered allowable; see Section [5.2.1](#) for further details.

6. INVESTIGATIONAL PRODUCT

6.1 Identity of Investigational Product

The test product is SHP639 ophthalmic solution, which will be provided as an ophthalmic solution packaged in 7.5 mL (filled to 5 mL) multiuse eye drop bottles. SHP639 ophthalmic solution is a sterile, colorless topical solution containing 0.1%, 0.3%, or 0.6% SRD006086 (as free-base equivalent). The SHP639 ophthalmic solution is preserved with benzalkonium chloride and will be supplied in a multiuse low-density polyethylene eye drop bottle. Additional information is provided in the current SHP639 IB.

The quantities of SHP639 drug substance per drop of SHP639 ophthalmic solution are shown in [Table 9](#).

Table 9 SHP639 Drug Substance per Drop of SHP639 Ophthalmic Solution

Topical Concentration (% weight/volume)	Quantity of SH639 Drug Substance per Drop (µg)
0.1	35
0.3	104
0.6	208

Quantities of drug substance per drop were calculated using a drop volume of 34.7 µL, which was the mean volume obtained at various temperatures, bottle orientations, and concentrations. Values have been rounded to the nearest microgram.

The reference product is placebo, which will be provided as an ophthalmic solution packaged in 7.5 mL (filled to 5 mL) multiuse eye drop bottles identical to those used for the SHP639 ophthalmic solution. The placebo solution will contain the same excipients as the SHP639 ophthalmic solution but will not contain SHP639.

6.1.1 Masking the Treatment Assignment

This is a double-masked, placebo-controlled study. The packaging, appearance, and labeling of the investigational products will match.

6.2 Administration of Investigational Products

6.2.1 Interactive Response Technology for Investigational Product Management

The actual treatment given to individual subjects is determined by a randomization schedule. The associated treatment assignments giving details of individual subject treatment are in the form of a randomization schedule created by the interactive response technology (IRT) vendor.

Each bottle/carton of SHP639 ophthalmic solution or matching placebo will be assigned a unique packaging identification number corresponding to the investigational product allocated to the subject, once eligibility has been determined. When a bottle/carton of SHP639 ophthalmic solution or matching placebo is assigned to a subject, the packaging identification number will be recorded in the eCRF and in the drug accountability records. Once assigned, it is important that the bottle/carton remains with the same subject throughout the study.

6.2.2 Allocation of Subjects to Treatment

This is a double-masked, placebo-controlled study.

Subject numbers are assigned to all subjects as they consent to take part in the study. Within each site (numbered uniquely within a protocol), the subject number is assigned to subjects according to the sequence of presentation for study participation. This will be a 4-digit number starting at 0001.

For screen failures, the screening number will be the identifying number used throughout the eCRF.

The actual treatment given to individual subjects is determined by a randomization schedule.

The randomization number represents a unique number corresponding to investigational product allocated to the subject and will be allocated before dosing after eligibility has been determined.

A randomization number is allocated before dosing once eligibility has been determined. Once a randomization number has been assigned, that number must not be used again, if for example, a subject is withdrawn from the study. If a randomization number is allocated incorrectly, the study monitor must be notified as soon as the error is discovered.

Replacement subjects are to be assigned the same treatment as subjects they are replacing.

Individual subject treatment is automatically assigned by the IRT.

Investigational product packaging identification numbers, separate from randomization numbers/unique identifiers, may also be assigned to subjects for specific treatment assignment as dictated by the study. In these cases, the same investigational product packaging identification number may not be assigned to more than 1 subject.

